10.4 FES intervention

FES Intervention will begin in week 10, once the pre-FES assessment has taken place and the FES desensitisation period is complete (see figure 1). FES intervention will end in week 18.

Each CYP will be asked to use the FES device for between 2-4 hours a day, 6 days a week, for 8 weeks. This duration has been guided by PPI feedback on the study protocol and a RCT on the use of FES in drop foot in children with CP [26]. The FES can be worn at home and or at school depending on the preferences of the CYP. The CYP will be asked to avoid starting any new physical activities or sports during the period of FES intervention but may continue with their usual physiotherapy routine.

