17. ADVERSE EVENTS

17.1 Recording and reporting of AEs

An adverse event (AE) is defined as any unfavourable and unintended sign that develops or worsens during the period of the trial, whether or not it is considered to be related to the trial. The risks of taking part in this trial have been assessed to be low.

Any new or worsening problems, which participants perceive to be related to participation in the study and occur at the single visit and within the following 48 hrs will be captured.

Examples of AEs that require reporting include:

- Aches and pains in the leg muscles following FES stimulation, lasting over 1 hour following cessation of the stimulation or requiring pain relief
- Fatigue following FES intervention lasting more than 1 day
- · Injury related to the study procedure or data collection
- Red marks or a reaction on the surface of the skin because of contact with FES electrode pads, which last for more than 10 minutes after data collection is complete.

Participant's parent and or guardian will be asked to report any AE's that occur for the duration of the study to the Cl/ SC. These will be gathered during the weekly face-to-face measurement sessions. Recorded AEs and SAEs will be presented at a

Health Research Authority

Study management Group (SMG) meeting for review. The SMG will refer concerns to the Study Steering committee (SSC) for further review if required. AEs considered related to study participation will be followed until resolution or the event is considered stable. If the AE occurs during the study assessment the Study Coordinator (SC) in discussion with the participant parents/Guardian will take responsibility as to whether an AE is of sufficient severity to withdraw the participant from the study. The participant may also voluntarily stop participating in the study if he or she perceives an incident to be an intolerable AE.

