17.3 Responsibilities

Study Co-ordinator (SC):

- Checking for AEs when participant attends study day.
- Ensuring that all SAEs are recorded and reported to the sponsor and CI within 24hrs of becoming aware of the event and provide further follow-up information as soon as available.
- Completion of the SAE form must include the PI's assessment of causality i.e.
 whether there is a reasonable causal relationship between the SAE and
 attending the study appointment. If incomplete information is available at the
 time of reporting, all appropriate information relating to the SAE should be
 forwarded to the CI as soon as possible.

Chief Investigator (CI) / delegate or independent clinical reviewer:

- Clinical oversight of the safety of patients participating in the study, including an ongoing review of the risk / benefit.
- Ensuring that SAEs are sent to the sponsor within 1 working day of initial reporting. Using medical judgement in assigning the SAEs seriousness, causality and whether the event was anticipated where it has not been possible to obtain local medical assessment.
- Review of specific SAEs in accordance with the trial risk assessment and protocol.
- Central data collection and verification of AEs, SAEs, according to the study protocol onto study database.

Health Research Authority

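### Section 17.3 judges SAE causality against attending an appointment rather than against FES, and Section 17.1 gives conflicting rules on which AEs are captured

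*Protocol*

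**What the plan says.** Protocol Section 17.1 makes three statements about which AEs count.

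- The definition covers "any unfavourable and unintended sign that develops or worsens during the period of the trial, whether or not it is considered to be related".
- The capture sentence covers new problems, or existing ones that get worse, "which participants perceive to be related to participation in the study and occur at the single visit and within the following 48 hrs".
- The reporting sentence says that parents or guardians are "asked to report any AE's that occur for the duration of the study", and adds: "These will be gathered during the weekly face-to-face measurement sessions".

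Section 17.2 records SAEs until the participant completes follow-up or withdraws. Any SAE is to be reported within 24 hours of the team becoming aware of it, and unexpected serious related events go to the REC within 15 days.

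Section 17.3 says the SAE form must include the PI's causality assessment and spells out what that means: whether there is a reasonable causal relationship between the SAE and "attending the study appointment".

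Under Section 10.4 (FES intervention), each child is asked to "use the FES device for between 2-4 hours a day, 6 days a week, for 8 weeks", at home or at school. Section 10.2 adds a build-up week of daily use before that.

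**The concern.** The exposure that could cause harm is the stimulation and walking with the device, and most of it happens away from the study team. A causality question that asks only about the appointment points at the wrong exposure. If a child fell while walking with FES at school and attended an emergency department, the event would be an SAE under Section 17.2. The truthful answer to the Section 17.3 question would nevertheless be that attending the appointment did not cause it. Relatedness decides which SAEs go to the REC within 15 days, so the wording could change what is reported onward.

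For non-serious AEs, the study co-ordinator is given rules that cannot all be followed. The capture sentence filters on perceived relatedness, which the definition rules out, and on a single visit, which this study does not have.

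The protocol intends to conclude on safety (Section 15.2) and to inform a later randomised trial (Section 2). With 12 children, one misattributed SAE is 1/12, about 8% of participants.

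**Working it through.** The protocol gives no figure to reproduce here. The check sets the sections side by side and adds simple arithmetic on exposure.

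1. **Is there a single visit?** No. Section 9 gives 16 weekly sessions, Section 7.3 adds impairment batteries at weeks 0, 8, 10 and 19, and Section 15.3 gives 20 weeks per participant.

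2. **Do the three statements in Section 17.1 agree?**

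| Statement | Relatedness filter | Time covered |
|---|---|---|
| Definition | none | whole trial |
| Capture sentence | perceived as related | one visit plus 48 hours |
| Reporting sentence | none | whole study, gathered weekly |

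The first and third agree. The second conflicts with both, on relatedness and on time. It also sits badly with the section's own examples: "Fatigue following FES intervention lasting more than 1 day" describes an effect of the intervention, not of a visit. The skin-reaction example is again timed from the end of data collection, not from the end of wear.

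3. **Where does FES exposure occur?** Inputs are Section 10.4 for use, Section 9 for 45-minute weekly sessions, and Sections 7.2 and 10.4 (Pre and Post FES assessment) for 90-minute assessments.
   - Planned use: 2 × 6 × 8 = 96 h at the low end; 4 × 6 × 8 = 192 h at the high end.
   - Contact around that phase: 8 × 0.75 + 2 × 1.5 = 9 h.
   - Counting every contact minute as stimulation within the planned hours, the share outside contacts is (96 − 9)/96 = 90.6% to (192 − 9)/192 = 95.3%.
   - This is a lower bound on the share outside, because sessions also include strength tests, questionnaires, and FES-off and AFO walking. The build-up week is not counted.

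4. **Does another section widen the causality question?** Not in the visible text. Section 17.3 lets the chief investigator use medical judgement on causality, but only where local medical assessment could not be obtained, and it does not restate the question. Sections 17.1 and 17.2 speak more broadly of events related to study participation or to the study, but neither says that this replaces the definition given for the SAE form.

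**The case against.** A reader might infer that AE capture is limited to one visit plus 48 hours, so that harm at home would go unrecorded. The protocol does not support that. Section 17.1 also asks for any AE over the whole study and gathers these weekly. Section 17.2 sets no 48-hour limit on SAEs. Every SAE goes to the sponsor and chief investigator within 24 hours whatever its cause, and AEs and SAEs are reviewed by the Study Management Group. For serious events the risk is misattribution, not loss. For other AEs it is uncertainty about which rule applies. A coverage fraction worked out from the 48-hour window would measure lost events only if the reporting sentence were ignored.

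It is also fair to say that FES is not absent from Section 17: three of the four AE examples name it. The REC trigger in Section 17.2 does not itself use the appointment wording, so an investigator might apply the broader sense of relatedness. The week-20 interview also asks about adverse effects while using FES. These points reduce the likely effect, but none changes what the SAE form is required to assess.

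A reader might also infer that the wording was carried over from a one-visit study. The protocol does not say so, and the point does not depend on it.

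The SAE form is not shown, and only the opening line of the Appendix 2 flow chart can be read. Either may already be worded differently.

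**Conclusion.** The point stands as two wording defects. The more important is in Section 17.3: the mandatory causality question names the appointment, while at least about 91% of planned FES hours fall outside study contacts. Read literally, it would class a serious harm from home or school FES as unrelated, and the event might then miss the 15-day REC report. The second is the contradiction in Section 17.1 on both relatedness and time window.

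This rests on staff applying the text as written and on no unseen document overriding it. The 91% describes where exposure occurs if planned use is achieved. It does not estimate how many events would be missed or misclassified, and the protocol gives no basis for such an estimate.

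**What to change.** - **Section 17.1:** delete the single-visit sentence or bring it into line, so that one rule applies: all AEs, whether or not perceived as related, for the study duration, collected at the existing weekly contacts. Align the timing in the skin-reaction example with that rule.
- **Section 17.3:** reword the causality question to ask separately about (a) the FES device or stimulation, including home and school use, and (b) the study assessments.
- **SAE form and Appendix 2 flow chart:** check that both agree with the revised text.

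The cost is a wording amendment and a few more minor AEs to log. No extra visits are needed.

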17.2 Recording and reporting of SAEs

Participants and the SC will be asked to report any SAEs directly to the CI as soon as possible via e-mail / Telephone call. A serious adverse event (SAE) is defined as an untoward occurrence that:

- (a) results in death;
- (b) is life-threatening;
- (c) requires hospitalisation (where hospitalisation is any admission leading to an overnight inpatient stay, or any day case appointment, or any ED attendance) or prolongation of existing hospitalisation;
- (d) results in persistent or significant disability or incapacity;
- (e) consists of a congenital anomaly or birth defect; or
- (f) Is otherwise considered medically significant by the investigator.

SAEs will be recorded until the date the participant completes follow-up or withdraws from the study. SAEs may be volunteered by the participant or discovered by the SC through questioning, physical examination or other investigation, or as a result of direct reporting (e.g. by telephone) by the participant, independent clinician or other informant. Participants will be asked to report any SAEs directly to the CI as soon as possible via e-mail / Telephone call.

SAEs will be followed until resolution/stable condition is reached. It is not anticipated that there will be any SAEs related to this study. Any SAE will be reported within 24 hours of the research team becoming aware of it. Any Unexpected Serious Related Events will be reported to REC within 15 days of CI being informed.

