During FES Set Up, the participant will experience the sensation of FES activating the muscle for the first time, for some CYP this can be uncomfortable to begin with. They will be given time to get used to the sensation and can stop for comfort breaks if required. If the CYP is unable to tolerate the sensation, they can ask to stop the session and may wish to withdraw from taking part in the study. Once the FES device is set to a level that a contraction is observed in either Tibialis Anterior or the Quadricep, the SC will stick the foot switch into a cork insole, which can then be placed in the child's shoe. In most cases the foot switch will be placed in the heel of the insole (see figure 8A), but if the child is not achieving a heel strike at initial contact, the foot switch will need to be placed under the head of the first metatarsal (see figure 8B). Once the foot switch is connected to the FES device the participant is ready to trial using the FES when walking. For FES tibialis anterior set up, the FES device will be set to activate tibialis anterior when the heel or forefoot rises off the floor and through swing phase of gait. For FES quadricep set up the device will be set to activate the quadricep at initial contact and early stance phase of gait. Once the child is walking with the FES the SC may have to make further adjustments to the timing and speed of the muscle activation for optimal gait performance

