12.6 Withdrawal

Participants can withdraw at any point in the study without giving a reason. It will be emphasised that this would not affect their healthcare or potential involvement in another research. At the point of withdrawal from the study CYP data up to that point will be used for data analysis unless the CYP and/or parent express that they would like this data to be destroyed.

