14.3 Archiving

Paper and electronic formats and essential study documentation (i.e content of Study Master file) will be store in a secure location for a minimum of 10 years after the end of the study. Archiving will be authorised by the Sponsor following submission of the end of study report. No essential documents should be destroyed unless or until the Sponsor gives authorisation to do so. This is in accordance with the University of Plymouth Research Data Management Policy which can be found here: https://plymouth.libguides.com/researchdatamanagement

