the number of sessions, their schedule, and their duration, intensity, or dose	children with CP [26]. The FES can be worn at home and or at school depending on the preferences of the CYP. The CYP will be asked to avoid starting any new physical activities or sports during the period of FES intervention but may continue with their usual physiotherapy routine
9. TAILORING if the intervention was planned to be personalised, titrated, or adapted, then describe what, why, when, and how.	The FES intervention including the frequency, pulse width and amplitude is tailored to the individual. It will be based on the clinical judgement of the SC, in accordance to the CYP muscle response to stimulation and in order to optimise gait performance. FES electrode pad placement for both Tibialis Anterior and Quadriceps may differ between individuals due to variations in anatomy, but electrode placement will remain the same for a CYP throughout the study.
10. MODIFICATIONS if the intervention was modified during the course of the study, describe the changes (what, why, when, and how).	Modification to the FES intervention may occur if the child has an adverse skin reaction or if they are finding it difficult to tolerate the FES stimulation
11. HOW WELL if the intervention was modified during the course of the study, describe the changes (what, why, when, and how).	To be explored post FES Intervention

NHS

Health Research Authority

References

- [1] P. Rosenbaum, N. Paneth, A. Leviton, M. Goldstein, and M. Bax, "A report: The definition and classification of cerebral palsy April 2006," in *Developmental Medicine and Child Neurology* vol. 49, ed, 2007, pp. 8-14.
- [2] M. Noorkoiv et al., "Predictors of Walking Efficiency in Children With Cerebral Palsy: Lower-Body Joint Angles, Moments, and Power," Physical Therapy, vol. 99, no. 6, pp. 711-720, 2019, doi: 10.1093/ptj/pzz041.
- [3] E. G. Fowler, L. A. Staudt, M. B. Greenberg, and W. L. Oppenheim, "Selective Control Assessment of the Lower Extremity (SCALE): development, validation, and interrater reliability of a clinical tool for patients with cerebral palsy," *Developmental Medicine & Child Neurology*, vol. 51, no. 8, pp. 607-614, 2009/08/01 2009, doi: https://doi.org/10.1111/j.1469-8749.2008.03186.x.

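### SAE recording closes on the day a child withdraws, no route exists to stop FES and stay in follow-up, and data destruction on request does not exempt safety records

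*Protocol*

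**What the plan says.** **Recording window.** Protocol 17.2: "SAEs will be recorded until the date the participant completes follow-up or withdraws from the study". Related AEs (17.1) and SAEs (17.2) are followed until they resolve or are stable, and neither sentence sets a cut-off at withdrawal. SAEs go to the sponsor and CI within 24 hours of awareness (17.3).

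**What follows a poorly tolerated event.** For an AE arising at an assessment, section 17.1 leaves it to the SC, after talking with the parents or guardian, to judge "whether an AE is of sufficient severity to withdraw the participant from the study". The same section also covers the child's own decision: "The participant may also voluntarily stop participating in the study if he or she perceives an incident to be an intolerable AE". Section 10.1, on a child who cannot tolerate the sensation at set-up: "they can ask to stop the session and may wish to withdraw from taking part in the study". Appendix 8 gives another response to skin reactions or to stimulation that is hard to bear: "Modification to the FES intervention may occur if the child has an adverse skin reaction or if they are finding it difficult to tolerate".

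**Data after withdrawal.** Section 12.6 keeps and analyses data up to withdrawal "unless the CYP and/or parent express that they would like this data to be destroyed". Section 14.3: "No essential documents should be destroyed unless or until the Sponsor gives authorisation to do so".

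**The concern.** The protocol has one status for leaving, which is withdrawal from the study, and the SAE window is tied to it. Whenever withdrawal is prompted by a reaction to FES, the date that ends treatment also ends the search for new serious events. Routine collection ends with it: AEs are gathered at the weekly measurement sessions (17.1), and the SC checks for them when the child attends (17.3).

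Section 15.2 uses the interviews to determine feasibility, acceptability and safety, and section 11.1 places them at week 20. A child who left because FES was intolerable has no planned interview, so that evidence could lean towards children who tolerated the device.

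Section 12.6 also permits records already made to be destroyed. Staff who receive such a request have no rule for AE and SAE records. Section 2 (Rationale) says the series is meant to inform a randomised trial, so its safety account should be as complete as families will allow.

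**Working it through.** The protocol states no figure on this point, so the check is mainly of the text.

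**1. Which events fall outside the window?**
- Event before or on the date of withdrawal: inside the 17.2 window if serious. It is followed to resolution or stability if serious or study-related, and kept by default under 12.6.
- New SAE after that date: outside the 17.2 window. The follow-to-resolution sentences do not help, because they apply to events already recorded. No contact after withdrawal is specified.

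The gap is therefore new SAEs that start after withdrawal.

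**2. Is there a route to stop FES and stay?**
- 17.1, AE during an assessment: the SC and parents consider withdrawal from the study.
- 17.1, AE the child finds intolerable: the child may stop taking part in the study.
- 10.1, intolerance at set-up: the child may stop the session and may wish to leave the study.
- Appendix 8: FES may be modified.

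None of these describes a child who stops FES and remains in follow-up. No section forbids it either.

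**3. Do 12.6 and 14.3 agree on safety records?** Section 12.6 allows destruction on request with no exemption. Section 14.3 requires essential documents to be kept for at least 10 years and bars destruction without sponsor authorisation. Section 14.1 treats the CRF as source data. Neither 12.6 nor 14.3 mentions the other, so whether AE and SAE records may be destroyed on request is undetermined.

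**4. Time outside the window.** The device is issued in week 9 (section 4) and the last contact is in week 20. Weeks without SAE recording = 20 − week of withdrawal:
- withdrawal at set-up: 20 − 9 = 11 weeks;
- withdrawal in week 12 (assumed): 20 − 12 = 8 weeks.

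This is calendar time. Nothing in the protocol suggests that FES use continues after withdrawal.

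**5. Illustration of one destroyed record.** Assume that one of 12 children has an AE-driven withdrawal and that the family also asks for destruction.
- Record kept: 1/12 = 8.3%, exact (Clopper-Pearson) 95% interval 0.2% to 38.5%.
- Record destroyed: 0/11 = 0%, upper limit 1 − 0.025^(1/11) = 28.5%.

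Both conditions are assumptions, and the documents give a rate for neither.

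**The case against.** A reader might infer that the children most harmed by FES drop out of the safety record. The documents do not support that. The harm that causes a withdrawal precedes it, so an SAE of that kind is within the window, is followed to resolution or stability and reaches the sponsor and CI within 24 hours. Data up to withdrawal are retained unless the family asks otherwise.

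A reader might also infer that withdrawal is the SC's set response to a severe AE. It is a judgement made with the parents, limited to AEs during an assessment, and Appendix 8 foresees modifying FES instead.

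Further points on the other side:
- Ending collection when a family chooses to leave respects that choice. This stands, which is why the fix makes an exception for refusal of contact.
- 14.3 may already protect SAE forms, if they count as essential documents. That is possible, but 12.6 does not say so and the two sections still need reconciling.
- AE incidence is not a listed objective or outcome. That limits the consequence, but 15.2 does claim to determine safety.
- The information sheet and the body of the Appendix 2 flow chart are not available here, so an exemption may be stated there. The wording of 12.6 and 17.2 would still need to match it.

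**Conclusion.** The point holds in a limited form. As written, SAE recording closes at withdrawal, so later-onset SAEs are not collected. Stopping FES is not distinguished from leaving the study, so a child who cannot tolerate it may miss later safety checks and the interview. Destruction on request carries no safety exemption and is not reconciled with 14.3.

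The size is modest and cannot be estimated from the documents. Each child is 1/12 = 8.3% of the denominator. The shift from 1/12 to 0/11 only illustrates the extreme case and needs both an AE-driven withdrawal and a destruction request. Selective loss of the worst reactions is not shown. This is a cheap improvement to safety reporting; the primary knee-angle analysis does not depend on it.

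**What to change.** - **17.2:** record SAEs to week 20, the study's existing end point, for every child issued a device, unless the family refuses further contact.
- **12.6 and 17.1:** distinguish stopping FES from withdrawing from the study. Invite children who stop FES to remain for safety contact and the week-20 interview. This concerns data collection only; it sets no rule for when FES should be stopped or modified.
- **12.6:** reconcile with 14.3 by exempting AE and SAE records from destruction on request, and state this in the information sheet so that families know before consenting.

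Cost: an amendment with ethics approval, revised information-sheet wording, and a few telephone contacts for children who stop early. The real downside is that families lose the option to erase safety records.
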